#### **4.1.3 TREATMENT VISIT 1 (TV1) (WEEK 4: DAY 28±3), TREATMENT VISIT 2 (TV2) (WEEK 8: DAY 56±3), TREATMENT VISIT 3 (TV3) (WEEK 12: DAY 84±3)**

The following assessments will be performed:

- Vital signs (Refer to [Section 8.5](#))
- Weight and BMI (Refer to [Section 8.6](#)) (Only at TV3)
- Physical examination (Refer to [Section 8.7](#))
- Laboratory assessments (hematology, biochemistry and urine analysis) (Refer to [Section 8.8](#))
- Electrocardiogram (Refer to [Section 8.9](#)) (This is done ONLY at TV1 and TV3)
- Urine pregnancy test (Refer to [Section 8.10](#)) (This is done ONLY at TV3)
- MDS-UPDRS Scale (Refer to [Section 8.11](#))
- Hoehn and Yahr (H&Y) Scale (Refer to [Section 8.12](#))
- Schwab and England (S&E) Scale (Refer to [Section 8.15](#))
- Parkinson's Disease Questionnaire (PDQ-39) total score (Refer to [Section 8.13](#))
- Clinical Global Impression-Severity (CGI-S) and Clinical Global Impression-Improvement (CGI-I) scale (Refer to [Section 8.16](#))
- List concomitant medications (Refer to [Section 7](#))
- Columbia-Suicide Severity Rating Scale (C-SSRS) (Refer to [Section 8.16](#))
- Adverse events evaluation (Refer to [Section 10](#))
- Study treatment dispensation (This is done ONLY at TV1 and TV2) (Refer to [Section 6.7](#))
- Study treatment accountability (Refer to [Section 6.9](#))

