DA-9805 has not undergone any clinical testing in the US or anywhere else in the world; the study proposed under this IND is the first-in-human study. Non-clinical study data summarized below provides safety data for conducting the first DA-9805 in-human study. The NOAEL of DA-9805 in rats was determined at 2000 mg/kg in males and 1000 mg/kg in females with stomach being the affected organ. Based on the FDA guidance on Estimating the maximum safe starting dose in initial clinical trials for therapeutics in adult healthy volunteers (2005), the human equivalent dose (HED) can be estimated from animal NOAEL using conversion factors based on body surface area, in which the

maximum recommended starting dose (MRSD) is then derived from by applying a safety factor. 1000 mg/kg NOAEL rat dose is equivalent to HED 161 mg/kg, or 9677 mg for a 60 kg adult. The proposed starting doses selected for the first in human clinical trial are 45 mg/day and 90 mg/day; highest selected dose, 90 mg/day, is not expected to result in safety issues based on the animal data and the applied safety factor of 100.

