**Table 4-1: Study Schedule of Events**

Study Parts	Screening Part (2 weeks)	Double-Blind Treatment Part (12 weeks)					Follow-up Part Follow-up Visit(4 weeks)
		TV0 Randomization		TV1	TV2	TV3	
Treatment Visits		Day 0					FUV
Weeks from Randomization Date (window period: ± days)	- 2	Pre-		Post-	+ 4 (± 3)	+ 8 (± 3)	+ 12 (± 3)
Written Informed Consent	X						
Inclusion/Exclusion Criteria	X						
Schedule Randomization Day	X						
Continued Eligibility		X					
Randomization		X					
Demographics	X						
Medical History	X	X					
Physical Examination	X	X		X	X	X	
Vital Signs	X	X	X	X	X	X	
Height  and Weight	X	X				X	
ECG	X	X		X		X	
Serum Hematology 	X			X	X	X	
Serum Chemistry 	X			X	X	X	
Urine Analysis 	X			X	X	X	
Urine Pregnancy Test 	X	X				X	
MDS-UPDRS		X		X	X	X	
H & Y	X	X		X	X	X	
S & E		X		X	X	X	
PDQ-39		X		X	X	X	
CGI-S and CGI-I 	X	X		X	X	X	
C-SSRS	X	X		X	X	X	
MMSE	X	X					
Dispense the DA-9805 or placebo 			X	X	X		
DA-9805 or Placebo first dose administration			X				
Study treatment accountability				X	X	X	

Study Parts	Screening Part (2 weeks)	Double-Blind Treatment Part (12 weeks)				Follow-up Part Follow-up Visit(4 weeks)	
Treatment Visits		TV0 Randomization		TV1	TV2	TV3	FUV
Weeks from Randomization Date (window period: $\pm$ days)	- 2	Day 0		+ 4 ( $\pm$ 3)	+ 8 ( $\pm$ 3)	+ 12 ( $\pm$ 3)	+ 16 ( $\pm$ 3)
Adverse Events			X	X	X	X	X
Concomitant medications	X	X		X	X	X	X

 Height only at Screening.

 Subjects who meet eligibility criteria, but have some abnormal laboratory values, based on PI review a repeat laboratory sample may be collected. The repeat laboratory reports should be reviewed by the PI to confirm eligibility prior to randomization.

 Only for female subjects of childbearing potential.

 CGI-I will be done only at Treatment Visit 1 to Treatment Visit 3

 Dispense the DA-9805 or placebo at each of the clinic treatment visit, except TV3 which is the End of Treatment visit (EOT).

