### 5.2 SUBJECT PREMATURE WITHDRAWAL FROM THE STUDY

A subject who is randomized into the study, but who does not complete the study will be considered prematurely discontinued.

All subjects have the right to withdraw at any point during the study without prejudice. It will be documented whether or not each subject completed the clinical study. If for any subject, study treatment or observations were discontinued, the reason(s) will be recorded and the Sponsor should be notified promptly. All efforts must be made to collect data and report records and tests as completely as possible. Reasons for subject withdrawal/discontinuation may constitute one of the following:

- Subject withdrew consent
- Subject chooses to withdraw
- Subject is withdrawn due to an AE
- Pregnancy
- Lost to follow-up
- Subject is treated with or takes a prohibited medication
- The Investigator determines that it is in the subject's best interest
- Excessive protocol deviations, as determined by the Investigator or the Sponsor
- Discontinuation of study by the Sponsor

For subjects who withdraw/are discontinued prematurely, TV3 assessments will be performed as the end of study evaluations. For all withdrawn/discontinued subjects the Follow-up visit will happen 4 weeks  $\pm 3$  days after the end of study Visit evaluations.

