#### **6.7 STUDY TREATMENT DISPENSATION**

At Treatment Visits 0, 1 and 2 of the study, sufficient randomized study treatments will be dispensed to each randomized subject for the period of time between the current clinic visit and the next clinic visit. Investigational products will be provided as blister packs. Each blister pack will contain 10 tablets of DA-9805 or placebo. For the active treatment group, 11 blister packs of active tablets (DA-9805 45mg or DA-9805 90mg as per treatment assignment) will be dispensed at each of these visits. For the placebo group, 11 blister packs of placebo tablets will be dispensed at each of these visits.

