## 7 CONCOMITANT AND PROHIBITED MEDICATIONS

Initiation of any new Parkinson's treatment during the study is prohibited.

Subjects must be questioned at each study visit concerning any new medications or changes in current medications including over-the-counter medication and topical medication. All medications and therapies administered or taken by the subject beginning 30 days prior to signing the ICF and throughout the study will be recorded in the source documents and on the appropriate page of the CRF.

For each medication and non-study treatment, the following will be documented:

- Medication/treatment name (generic name may be used if trade name is unknown)
- Dose, unit, and frequency of dosing (individual dosages, not total daily dose). Note: Each new dose of medication should be recorded as a separate entry, with the exception of medications that are given on a sliding scale. For these, it is acceptable to enter the range of the dosage, including the start and stop dates for which the specified dosage range was used.
- Route of dosing
- Indication for use
- The start date
- The stop date (if medication/therapy is not ongoing)

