## 8.10 URINE PREGNANCY TEST

The result must be documented on the source documents and in the CRF. Subjects who are found to be pregnant during the screening period will be considered a screen failure. If pregnancy occurs during the course of the study, the subject will be withdrawn from the study and the pregnancy will be followed up to term for safety purposes. Relevant safety information collected after the study has completed will be reported as supplemental information.

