### 13.3 MODIFICATION OF PROTOCOL

The Investigator will not modify or alter this protocol without first obtaining the concurrence of the Sponsor. Approval by the Investigator's IRB must also be obtained prior to implementation of the change, with two exceptions:

1. When necessary to eliminate apparent immediate hazard to the subject; or
2. When the modification does not involve the subject's participation in the trial.

An amendment may also require modification of the ICF. The Investigator will provide an approval letter for the amendment and revised ICF, if applicable, to the Sponsor. An amendment must be in

---

writing and it must be dated by both the Sponsor and the Investigator. If necessary, the Sponsor will submit protocol amendments to FDA and other appropriate regulatory authorities and notify other Investigators using this protocol.

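### For women who complete treatment, no pregnancy test is scheduled between Day 0 and TV3, although drug is re-dispensed at TV1 and TV2; adding the existing urine test there is a cheap, low-severity improvement

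*Protocol*

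**What the plan says.** Protocol Table 4-1, Protocol Sections 4.1.1 to 4.1.3 and SAP Appendix 1 agree. The urine pregnancy test is done at Screening, at TV0 before randomization, and at TV3, for women of child-bearing potential only. For the on-treatment visits, Section 4.1.3 says "This is done ONLY at TV3".

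Section 8.10 gives the consequence of a positive result: "If pregnancy occurs during the course of the study, the subject will be withdrawn from the study". It sets no testing interval. Section 5.2 also lists pregnancy among the reasons for withdrawal.

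On supply, Section 6.7 says "At Treatment Visits 0, 1 and 2 of the study, sufficient randomized study treatments will be dispensed to each randomized subject". Neither that section nor Table 4-1 makes the TV1 or TV2 supply depend on a pregnancy test.

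Women who stop early are covered separately in Section 5.2: "For subjects who withdraw/are discontinued prematurely, TV3 assessments will be performed as the end of study evaluations". Those assessments include the pregnancy test, so the point concerns only women who go on to TV3.

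**The concern.** Section 8.10 intends that a woman who becomes pregnant leaves the study. TV3 is both the end of treatment and the visit that defines completion (Section 5.1), so a positive test there comes when dosing is already over. For a woman who stays in the trial, no scheduled test can trigger the rule while she is still taking tablets, and she receives two further supplies in that time.

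What is at stake is participant safety. Section 1.4 states that "the study proposed under this IND is the first-in-human study", and describes DA-9805 as the first mixture of these three botanicals. Continued dosing through an undetected pregnancy is what the withdrawal rule is meant to avoid. Sample size, the type I error rate and the efficacy analysis are not touched.

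**Working it through.** **Inputs.** TV0 is Day 0 (Protocol Section 4). TV1 is Day 28 ± 3, TV2 is Day 56 ± 3 and TV3 is Day 84 ± 3 (Section 4.1.3). Dosing is one tablet three times daily (Section 6.6). Eleven blister packs of 10 tablets are dispensed per visit (Section 6.7). The windows are Day 25 to 31, Day 53 to 59 and Day 81 to 87. Tablet counts assume full adherence.

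**1. Gap under the current plan**
- 12 weeks × 7 = 84 days, which matches the plan's Day 84. With the window it is 81 to 87 days.
- Tablets between the two tests: 84 × 3 = 252 (81 × 3 = 243 to 87 × 3 = 261).
- Re-supplies inside the gap: two, at TV1 and TV2.

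**2. Gap with tests at TV1 and TV2**
- Day 0 to TV1: 25 to 31 days.
- TV1 to TV2: 53 − 31 = 22 to 59 − 25 = 34 days.
- TV2 to TV3: 81 − 59 = 22 to 87 − 53 = 34 days.
- Longest gap: 28 days nominal, 34 at most.
- Tablets between tests: 28 × 3 = 84 nominal, 34 × 3 = 102 at most. Each dispensing is 11 × 10 = 110 tablets, so supply would not cut this short.
- Mean wait to the next scheduled test, if a pregnancy starts at a random time and the lag before a urine test turns positive is ignored: 84 / 2 = 42 days now, 28 / 2 = 14 days with the added tests.

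**3. Most that one detected case could gain**

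| Positive at | Days of dosing avoided | Tablets avoided |
|---|---|---|
| TV1 | 84 − 28 = 56 (81 − 31 = 50 to 87 − 25 = 62) | 168 (150 to 186) |
| TV2 | 84 − 56 = 28 (81 − 59 = 22 to 87 − 53 = 34) | 84 (66 to 102) |

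These are upper bounds. They need a pregnancy already detectable at the visit, one that would otherwise stay unrecognised or unreported until TV3, and full adherence.

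**4. How often the added tests might matter**

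The documents give neither the number *m* of women of child-bearing potential nor a pregnancy rate. Both are assumed below. With *r* the annual rate, p = 1 − (1 − r)^(56/365.25) is the chance for one woman in the first 56 days, and P(at least one) = 1 − (1 − p)^m. Only pregnancies starting in those 56 days could be found at TV1 or TV2.

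| Assumed *m* | r = 1% per year | r = 10% per year |
|---|---|---|
| 1 | 0.2% | 1.6% |
| 3 | 0.5% | 4.7% |
| 5 | 0.8% | 7.8% |
| 10 | 1.5% | 14.9% |

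For given assumptions, these overstate the chance that a test changes anything. They ignore the lag before a test turns positive, and they count pregnancies that the woman would have reported anyway. If *m* = 0, the chance is zero.

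**5. What else could reveal a pregnancy at TV1 or TV2**
- Adverse events are elicited by direct questioning (Section 10.1).
- Section 7 adds: "Subjects must be questioned at each study visit concerning any new medications or changes in current medications". Stopping a hormonal contraceptive could surface this way.
- There is a physical examination, but it leaves out the genitourinary system (Section 8.7).
- The laboratory panel lists no hCG (Section 8.8).
- Unscheduled visits are at the investigator's discretion, with no pregnancy test specified (Section 4.3).

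Each of these can help. None is a pregnancy test.

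**The case against.** The strongest reply is that nothing is broken. The two schedules and the text agree, the restriction to TV3 is explicit and so deliberate, and Section 8.10 sets no interval that the schedule could breach. No passage says that 84 days is too long or that 28 is right. This stands: a reader might infer an internal contradiction, and the documents do not support that.

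Safeguards are also in place. Pregnant women are excluded, two tests precede dosing, and reliable contraception is required (Section 3.1.2). TV1 and TV2 are full clinic visits with questioning and examination, and a DSMC considers safety data (Section 12). This stands too. It would be wrong to say that the rule rests on self-report and unscheduled visits alone. What remains uncovered is a contraceptive failure that is not recognised or not reported.

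A reader might infer a known reproductive hazard. The documents describe none. Section 1.4 reports long human use of the components and negative genotoxicity tests. Its summary describes no reproductive toxicity study, but that does not show that none was done.

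The saving of 56 days or 168 tablets could be read as typical. It is an extreme case, and subjects on placebo (one third by design) take no DA-9805 at all.

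Finally, the change is cheap only if another amendment carries it, and the documents show none pending. That also stands and is counted in the cost.

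**Conclusion.** The point holds in a narrow form, at low severity. For women who complete treatment, no pregnancy test is scheduled for 84 days (81 to 87), and drug is re-dispensed twice within that time. During dosing the Section 8.10 rule can be triggered by visit questioning or examination, by the woman's report, or by an unscheduled visit, but never by a scheduled test. Tests at TV1 and TV2 would reduce the longest gap to 28 days nominal, 34 at most.

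The gap lengths follow directly from the schedule. The tablet counts assume full adherence. The per-case savings of up to about 56 days (TV1) and 28 days (TV2) also assume a pregnancy that would otherwise go unrecognised or unreported.

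The expected benefit cannot be computed. With 60 subjects of both sexes aged 30 to 79, few women may be eligible, possibly none. A reader might infer that the chance of needing the tests is low. That is a reasonable judgement, but the documents do not establish it: across the assumed inputs above, the chance of a pregnancy starting in the first 56 days runs from 0.2% to 14.9%. The added tests would not prevent exposure before a test turns positive.

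**What to change.** In Protocol Table 4-1, Protocol Section 4.1.3 and SAP Appendix 1, add the existing urine pregnancy test at TV1 and TV2 for women of child-bearing potential, with the result known before study drug is dispensed at that visit. Leave Section 8.10 unchanged. No test is needed at the follow-up visit for this purpose, because dosing has ended and a test there cannot shorten exposure.

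**Cost.** Two dipsticks per eligible woman, so 2 to 20 tests for an assumed 1 to 10 women, at visits where urine is already collected; the documents give no prices. Sites must also test before dispensing, which fixes the order of the visit. The schedule change needs a protocol amendment with IRB approval across up to 10 centers. Consent may be affected as well, since Section 13.3 notes: "An amendment may also require modification of the ICF". It is best carried in the next amendment made for another reason; the added cost is then mainly the dipsticks and the visit-order step.

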## **4.2 FOLLOW-UP**

### **4.2.1 FOLLOW-UP VISIT (WEEK 16: DAY 112±3)**

The following assessments will be performed:

- List concomitant medications (Refer to [Section 7](#))
- Adverse events evaluation (Refer to [Section 10](#))

#### **4.3 UNSCHEDULED VISITS**

Unscheduled visits may be required in addition to the scheduled visits per the Investigator's discretion. The details of these unscheduled visits with subjects will be recorded in the medical records and on the Case Report Form (CRF).

#### **4.4 MISSED VISITS**

If a subject misses a visit, the site is to make every effort to have the subject return as soon as possible to make up the visit. Once the subject is seen, he/she is to return to his/her original visit schedule.

## 5 SUBJECT COMPLETION AND WITHDRAWAL

### 5.1 SUBJECT COMPLETION

A subject who completes TV3 will be considered to have completed the study.

### 5.2 SUBJECT PREMATURE WITHDRAWAL FROM THE STUDY

A subject who is randomized into the study, but who does not complete the study will be considered prematurely discontinued.

All subjects have the right to withdraw at any point during the study without prejudice. It will be documented whether or not each subject completed the clinical study. If for any subject, study treatment or observations were discontinued, the reason(s) will be recorded and the Sponsor should be notified promptly. All efforts must be made to collect data and report records and tests as completely as possible. Reasons for subject withdrawal/discontinuation may constitute one of the following:

- Subject withdrew consent
- Subject chooses to withdraw
- Subject is withdrawn due to an AE
- Pregnancy
- Lost to follow-up
- Subject is treated with or takes a prohibited medication
- The Investigator determines that it is in the subject's best interest
- Excessive protocol deviations, as determined by the Investigator or the Sponsor
- Discontinuation of study by the Sponsor

For subjects who withdraw/are discontinued prematurely, TV3 assessments will be performed as the end of study evaluations. For all withdrawn/discontinued subjects the Follow-up visit will happen 4 weeks  $\pm 3$  days after the end of study Visit evaluations.

#### **Important Notes:**

1. Subjects may drop out or be withdrawn at their own request. Although subjects do not need to give a reason for requesting withdrawal from the trial, the Investigator should make a reasonable effort to ascertain the reason(s), while fully respecting the subject's rights.
2. Any subjects reporting Serious Adverse Events (SAEs) that have not resolved by their last study visit will be followed to resolution or until 30 days after the subject completes the study.
3. Every attempt should be made to collect follow-up information. The reason for withdrawal from the study (if known) will be recorded in the source documents and on the appropriate page of the CRF.
4. Before a subject is identified as lost-to-follow-up, the site should make all reasonable efforts to contact the subject. These attempts must be documented and should include at a minimum one phone call and one follow-up certified letter.

### 5.3 SCREEN FAILURES

A subject who has signed the consent form but is not randomized is classified as a screen failure. Subject number, demographic information, and reason for screen failure will be collected.

## 6 STUDY TREATMENTS

### 6.1 METHOD FOR ASSIGNING ELIGIBLE SUBJECTS TO TREATMENT

Study eligible subjects will be randomized based on a randomization schedule prepared by Amarex Clinical Research, as the contracted CRO. Details of the randomization and assignment of the subject number are provided in [Section 4.1](#) and [Section 9.4](#).

At Baseline/Randomization visit (Treatment Visit 0, Day 0), all eligible subjects will be randomized 1:1:1 to receive DA-9805 at 45mg, 90mg or Placebo for 12 weeks.

After a subject has been determined to be eligible for the treatment in the study, a randomization number will be assigned. Once the randomization number is assigned, it cannot be re-assigned even if the subject is subsequently deemed ineligible or withdraws consent.

A subject who is randomized to study treatment becomes part of the Intent-to-Treat (ITT) population. Once a subject is randomized to study treatment, the subject must either complete the protocol or withdraw from the protocol (with reason specified). Randomized subjects may not be considered screen failures.

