## **6.9 STUDY DRUG COMPLIANCE**

Subjects will be instructed to bring used/unused study treatment blister packs. At each of these visits, tablet counts of returned study treatments will be conducted to determine if the subject has taken the study treatment per the protocol. If the number of dispensed tablets minus the number of remaining tablets (<80%) indicates that the subject is not taking their study treatment according to the study protocol, this will be recorded as a study drug non-compliance and the subject will be re-instructed on proper dosing. If the subject continues to be non-compliant with the dosing regimen the subject might be withdrawn from the study per the PI and/or the Sponsor's discretion. During Visits 1 to 3 subjects are required to report the date and time for the last daily dose of study treatment taken since the last visit.

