### 10.2.1 IMPACT ON STUDY TREATMENT

The impact the event had on the study treatment will be assessed as either: none, study treatment interrupted, study treatment discontinued, or not applicable. The "not applicable" assessment will be used only when the subject is no longer in the treatment phase of the protocol, or if the outcome of the event was "death".

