### **13.4 REPORTING PROTOCOL DEVIATIONS**

The Investigator is obligated to follow the protocol without departure from the requirements written in the protocol. If the Investigator deviates from the protocol requirements, the Sponsor will make the determination as to whether the subject will continue in the study. The Sponsor also has the right to discontinue the subject for protocol violations. The IRB may also have to be contacted if safety to the subject or if the scientific soundness of the study is involved. All protocol deviations must be documented in the CRFs.

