8.3.1 Adverse Events

Adverse events will be coded using the most recent version of Medical Dictionary for Regulatory Activities (MedDRA). Treatment Emergent AE's (TEAE) are defined as events with an onset on or after the first randomized treatment. TEAEs will be summarized by treatment group, System Organ Class, and preferred term. The following TEAE summaries will be provided:

- Overall (*i.e.*, regardless of severity or relationship to treatment)
- By severity grade (mild, moderate, severe, life threatening or death for SAEs)
- By relationship to clinical trial treatment according to the mapping scheme below:
 - Potentially related: will include all adverse events with a relationship rating of “definitely”, “probably” or “possibly”.
 - Unlikely/not related: will include all adverse events with a relationship rating of “unlikely” or “unrelated”.

Unless otherwise specified, at each level of subject summarization, a subject will be counted only once. If there is more than one occurrence of an event, the event of the worst severity or the worst-case relationship category will be summarized.

In addition, separate summaries of serious adverse events, and adverse events resulting in discontinuation of study treatment will be presented.

AEs leading to premature discontinuation of clinical trial treatment, AEs that lead to study discontinuation, AEs that lead to death and Serious Adverse Events (SAEs) will also be summarized by treatment group and relationship.

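### The protocol gives subjects who stop study drug no described route to their week-12 visit, and the SAP does not say how early exit scores are used

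*Protocol*

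**What the plan says.** Protocol 6.1 names two outcomes after randomization: "Once a subject is randomized to study treatment, the subject must either complete the protocol or withdraw from the protocol". Protocol 5.2 has one list of reasons covering both withdrawal and discontinuation, and one pathway: "For subjects who withdraw/are discontinued prematurely, TV3 assessments will be performed as the end of study evaluations". A follow-up visit comes 4 weeks (±3 days) after that. Protocol 4.2.1 limits its content to concomitant medications and adverse events.

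Subjects can also be removed at others' discretion. Protocol 6.9 says "If the subject continues to be non-compliant with the dosing regimen the subject might be withdrawn from the study", and Protocol 13.4 says "The Sponsor also has the right to discontinue the subject for protocol violations".

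Other passages treat drug and study as separable:
- Protocol 5.1 defines completion by the visit alone: "A subject who completes TV3 will be considered to have completed the study".
- Protocol 5.2 names the two as alternatives: "If for any subject, study treatment or observations were discontinued, the reason(s) will be recorded".
- The adverse-event action categories in Protocol 10.2.1 are "none, study treatment interrupted, study treatment discontinued, or not applicable".
- SAP 8.3.1 plans separate summaries: "AEs leading to premature discontinuation of clinical trial treatment, AEs that lead to study discontinuation".

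On analysis, SAP 8.2.1 compares each active group with placebo by ANCOVA on the week-12 change in motor MDS-UPDRS. The PP population is primary and the ITT population supportive (SAP 8.2). SAP 7.3.1 plans no imputation for efficacy. SAP section 7 has no visit-window rule.

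**The concern.** No passage describes scheduled visits through week 12 for someone who has stopped tablets but is willing to attend. A site following 5.2 and 6.1 would take that subject through one exit visit and out. A site relying on 5.1 might keep the subject coming to TV3. The documents support both practices, so the content of the week-12 data may depend on the site.

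The first practice leaves a gap that analysis cannot fill. An early leaver with an exit MDS-UPDRS meets the ITT definition in SAP 6.1 (one dose and one post-randomization efficacy assessment) but has no week-12 score. If the subject is dropped from the model, the supportive ITT analysis moves towards a completers' analysis, and so tests the consistency of the PP result less well. If the exit score is used because it carries the TV3 label, a value from another time point stands in for week 12.

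This matters because some listed reasons for leaving can depend on arm and outcome. Adverse events are one. Use of a prohibited medication is another, and Protocol 7.1 counts the start of Parkinson's treatment as that.

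**Working it through.** **The plan's own figure.** Protocol 9.3 and SAP section 4 give 20 per group: 3 × 20 = 60, which agrees. The number rests on clinical judgment. No effect size, SD, power or dropout rate is stated, so nothing further can be reproduced.

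**Timing.** TV1 is day 28, TV3 is day 84 ±3 (Protocol 4.1.3), and follow-up is exit + 28 days.
- Exit at day 28: follow-up at 28 + 28 = day 56, with no efficacy assessment.
- The exit score is 84 − 28 = 56 days before nominal week 12, and 81 − 28 = 53 days before the TV3 window opens.
- For any exit before day 84 − 28 = 56, the nominal follow-up also falls before week 12.
- An exit close to day 84 gives a score that is close to a week-12 value.

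**Bias (illustration; rates and gap are assumptions).** Let a fraction *f* of an arm stop, and let their week-12 change be *D* worse than that of those who stay. The full-arm mean is the stayers' mean + *f* × *D*, so the stayers' mean alone is too favourable by *f* × *D*.
- One arm, *D* = 5 points: 0.10 × 5 = 0.5 point; 0.20 × 5 = 1.0 point.
- Treatment difference: (*f* active − *f* placebo) × *D*. With 15% against 0%: (0.15 − 0) × 5 = 0.75 point.
- Equal stopping with an equal gap: 0 bias in the difference.
- In SD units: (0.10 − 0.05) × 0.5 = 0.025 SD at the low end; (0.30 − 0.10) × 1.0 = 0.20 SD at the high end.

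**Precision (illustration; unadjusted two-group comparison, two-sided 0.05).** Detectable difference at 80% power = (1.960 + 0.842) × √(2/n). The 95% CI half-width is t(0.975, 2n − 2) × √(2/n). Both are in SD units.

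| Lost per arm (assumed) | n | Detectable difference | Power at 0.886 SD | CI half-width |
|---|---|---|---|---|
| 0% | 20 | 0.886 | 80.0% | 0.64 |
| 10% | 18 | 0.934 | 75.7% | 0.68 |
| 20% | 16 | 0.991 | 70.7% | 0.72 |
| 30% | 14 | 1.059 | 65.0% | 0.78 |

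Retaining off-drug subjects restores n, but their scores may dilute a drug effect, so not all of this power would come back.

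**The case against.** The sentence in Protocol 6.1 does not mention stopping drug. It stands in the section on treatment assignment, beside the statement that randomized subjects cannot be screen failures, and can be read as a disposition rule. Protocol 5.1, the alternative wording in 5.2, Protocol 10.2.1 and SAP 8.3.1 all leave room for a subject to be off drug and still in the study. This stands. A reader might infer that the plan equates stopping drug with leaving, but no passage says so. What the documents show is a missing pathway and texts that need reconciling.

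A reader might also infer that the week-12 value is lost for every subject who stops, or that the losses are precisely the subjects who do not tolerate or do not benefit. Neither is supported. The exit visit carries the full TV3 set, including MDS-UPDRS, and a late stopper's score may be close to week 12. The reasons in 5.2 include pregnancy, loss to follow-up, the subject's own choice, deviations and closure by the sponsor. Lack of efficacy is not listed and enters only indirectly, through prohibited medication.

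A safety argument, that recovery after stopping goes unseen, is weak too. Completers also have no scheduled laboratory, ECG or vital-sign assessment after TV3. Clinically significant abnormalities are adverse events (Protocol 10.1), events are followed to resolution or until 30 days after the subject completes the study (10.2), and serious events until they normalise or stabilise (10.6).

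Finally, the primary objective is safety, the sample size is justified for descriptive results, and the primary efficacy analysis is PP, so better retention mainly helps a supportive analysis. That is largely right. However, stopping for an adverse event is not stated to be a major violation, so some of these subjects may also belong to the PP set. The ITT analysis is the plan's only stated check on the PP result.

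**Conclusion.** The point holds as a low-cost improvement. The protocol describes no path for a subject who stops drug to stay in scheduled visits to week 12. Its passages on stopping treatment and leaving the study must be reconciled, and the SAP leaves open whether an early exit score is omitted or analysed as week 12.

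The resulting bias cannot be sized from the documents. The 0.75-point figure depends entirely on the assumed stopping rates and the assumed 5-point gap. The range of 0.025 to 0.20 SD depends on similar assumptions. The bias disappears if stopping and the gap are equal across arms. With 20 per arm, each lost subject is 1/20 = 5% of the arm, so a few unequal exits would be enough to matter for interpretation.

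**What to change.** **Protocol 5.2 and 6.1.** Define two separate statuses, *discontinued study treatment* and *withdrew from study*. Keep the assessment at the time of stopping. Invite subjects who stop drug but still consent to attend their remaining scheduled visits through week 12 and the follow-up visit. Exempt study termination, and leave the pregnancy rule in Protocol 8.10 as it is. Record the date of last dose and the start of any Parkinson's medication.

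**Protocol 5.2, 6.9 and 13.4.** Reconcile these so that removal for non-compliance or deviations does not by itself end outcome collection. Who stops drug, and when, is not changed.

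**SAP.** State that flagged off-drug week-12 scores enter the ITT analysis and that an early exit score is not analysed as week 12. Give the exit assessment its own visit label, so that it cannot be taken for a duplicate TV3 under SAP 7.2.

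**Cost.** A protocol amendment, a CRF flag, and possibly one extra assessment at stopping. The remaining visits are already on each subject's schedule. Some subjects will decline them, so missing week-12 data will be reduced but not removed.
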